**Revision History**

[REDACTED]	[REDACTED]	[REDACTED]
[REDACTED]	[REDACTED]	[REDACTED]
[REDACTED]	[REDACTED]	[REDACTED]
[REDACTED]	[REDACTED]	[REDACTED]

**1 PROTOCOL SYNOPSIS**

Protocol Title	A Prospective, Multicenter Study of the OMNI® Surgical System in Pseudophakic Eyes with Open Angle Glaucoma (ORION)
Protocol ID Number	#06807
Study Device	OMNI® Surgical System
Study Objective	To prospectively assess the clinical effect of ab-interno transluminal viscoelastic delivery and trabeculotomy performed with the OMNI Surgical System in pseudophakic eyes on intraocular pressure (IOP) and the use of IOP-lowering medications in patients with open angle glaucoma (OAG).
Study Design	Prospective, multicenter, single-arm, post-market study
Primary Effectiveness Endpoint	
 
Proportion of eyes with a <math>\geq 20\%</math> decrease in unmedicated mean diurnal IOP (DIOP) at the 12-month (or 12-month washout) postoperative examination
 

[REDACTED]	[REDACTED]
[REDACTED]	[REDACTED]
[REDACTED]	[REDACTED]
[REDACTED]	[REDACTED]

Inclusion Criteria	
Inclusion Criteria (At least one eye of each subject should pass the ocular eligibility criteria listed below. Only one eye of each subject is eligible to receive the study procedure):
 

1. Male or female subjects, 22 years or older at the time of surgery

2. History of uncomplicated cataract surgery and posterior chamber IOL implantation without compromise to the lens capsule, zonular dehiscence/rupture or vitreous prolapse, 6 months or more prior to Baseline Visit.

3. [REDACTED]

6. Scheduled for ab-interno transluminal viscoelastic delivery and trabeculotomy using the OMNI Surgical System.

7. Shaffer grade of <math>\geq</math> III in all four quadrants

8. Able and willing to comply with the protocol, including all follow-up visits.

9. Understands and signs the informed consent

---------------------------	---

 For combination IOP-lowering medications that consist of two or more IOP-lowering drugs, each IOP-lowering drug component counts as a separate medication.

Exclusion Criteria	
A subject who meets any of the criteria listed below will not receive the study procedure. Ocular criteria are applicable to study eye and non-ocular criteria are subject-related:
 

1. Any of the following prior treatments for glaucoma:

○ Laser trabeculoplasty <math>\leq 3</math> months prior to Baseline visit

○ iStent or iStent Inject implanted <math>\leq 6</math> months prior to Baseline visit

○ Endocyclophotocoagulation (ECP) or Micropulse laser <math>\leq 6</math> months prior to Baseline visit

○ Trabeculectomy or other bleb forming procedure including Xen, Express, glaucoma draining device/valve

○ Prior canaloplasty, goniotomy, or trabeculotomy

○ Hydrus microstent

○ Suprachoroidal stent (e.g. Cypass, iStent Supra)

2. Acute angle closure, traumatic, congenital, malignant, uveitic or neovascular glaucoma

3. Concurrent IOP-lowering procedure other than use of the OMNI Surgical System at the time of surgery (e.g. ECP, CPC, etc.)

4. In the Investigator's judgement, predisposed to significant risk because of washout of ocular hypotensive medications

5. Concurrent ocular pathology or systemic medical condition which, in the Investigator's judgment, would either place the subject at increased risk of complications, contraindicate surgery, place the subject at risk of significant vision loss during the study period (e.g., wet AMD, corneal edema, Fuch's dystrophy, active intraocular infection or inflammation within 30 days prior to Screening Visit, etc.), or interfere with compliance to elements of the study protocol (e.g., returning to Investigator's office for follow-up visits).

6. History of penetrating keratoplasty or another corneal transplant

7. BCVA of logMAR 1.0 (20/200) or worse in the fellow eye not due to cataract

---------------------------	---

	
8. BCVA of logMAR 0.4 (20/50) or worse in the study eye not due to posterior capsular opacification (uneventful Nd:YAG laser capsulotomy 6 months prior to baseline is permitted only if there is no vitreous present in or in front of the iris plane at the time of baseline).
 
9. Participation (<math>\leq 30</math> days prior to baseline) in an interventional trial which could have a potential effect on the study outcome, as determined by the study investigator
 
10. Women of childbearing potential if they are currently pregnant or intend to become pregnant during the study period; are breast-feeding; or are not in agreement to use adequate birth control methods to prevent pregnancy throughout the study

Number of Subjects Enrolled and Treated	[REDACTED]
Number of Sites	[REDACTED]
Study Duration for Each Subject	[REDACTED]
Total Study Duration	[REDACTED]
Schedule of Visits	[REDACTED]
Treatments	Ab-interno transluminal viscoelastic delivery and trabeculotomy using the OMNI Surgical System as a standalone procedure in pseudophakic eyes

## 2 STUDY OBJECTIVE

To prospectively assess the clinical effect of ab-interno transluminal viscoelastic delivery and trabeculotomy performed with the OMNI Surgical System in pseudophakic eyes on intraocular pressure (IOP) and the use of IOP-lowering medications in patients with open angle glaucoma (OAG).

### 3 BACKGROUND AND JUSTIFICATION FOR THE STUDY

Glaucoma is a progressive disease leading to irreversible damage to retinal ganglion cells with the global burden expected to rise to 111.8 million people by the year 2040. OAG is the most prevalent form of glaucoma and it's proven that lowering IOP is the only efficient way to slow down the progressive optic nerve damage and visual field loss. Hypotensive eye drops are commonly used as the first line clinical management for OAG. Ocular side effects such as allergies, ocular surface disorders, blepharitis, pemphigoid, abnormal pigmentation etc. and systemic side effects such as bradycardia, headaches, depression, anxiety, confusion, dysarthria, hallucinations, lethargy, polyuria, weight loss, metabolic acidosis, etc. can occur during long term use of topical medications for management of OAG. There is also a documented low rate of compliance and tolerability with eye drops that results in disease progression and loss of vision. The cost of these chronic medications and difficulty administering drops to the eyes contributes to poor compliance.

Trabeculectomy and tube-shunt implantations remain the gold standard for surgical management of IOP. These interventions are associated with a long list of potential complications such as sclero-conjunctival scarring, hypotony, hypotony maculopathy, choroidal detachment, conjunctival leak, hyphema, and bleb related complications. Surgical techniques that re-establish the aqueous outflow through the physiological pathways without the need for a bleb are gaining acceptance among glaucoma surgeons. Delivering viscoelastic in Schlemm's canal is one such procedure that is intended to restore the natural aqueous outflow system through microcatheterization and viscodilation of the entire length of the Schlemm's canal with a well-documented

---

 European Glaucoma Society. Terminology and guidelines for glaucoma 4th edition Savona, Italy: Editrice PubliComm, 2014.

## 4.2 DEVICE DESCRIPTION

[figure not shown]
The OMNI™ Surgical System (“OMNI”) is a sterile, single use, manually operated instrument used by ophthalmologists to deliver small, controlled amounts of viscoelastic into the anterior segment of the eye during ophthalmic surgery. It is also indicated to cut trabecular meshwork tissue during trabeculotomy procedures.

The OMNI is designed to function with commonly used viscoelastic fluids made commercially available by companies such as Abbott Medical Optics (AMO), Bausch & Lomb, and Alcon. The OMNI dispenses fluid on the principle of exchanging volumes much like a syringe. The handheld instrument includes a cannula, microcatheter, internal reservoir and plunger tube, and finger wheels. The finger wheels on the handle of the device are used to advance and retract the microcatheter. In addition, when the device is being used to deliver viscoelastic, retraction of the microcatheter causes the plunger tube to advance into the viscoelastic fluid reservoir thereby dispensing viscoelastic fluid.

The microcatheter can be advanced/retracted up to 20 mm per cycle. The microcatheter can be fully advanced/retracted up to 5 times (i.e. 5 full cycles of 20 mm each). Dispensation of viscoelastic can only occur during the first two 20-mm cycles.

One finger wheel is located on the top and bottom of each device handle. This allows the OMNI device to be used in either eye (OD or OS) and in either hand of the surgeon (left or right), by turning the device 180 degrees along its vertical axis.

**Figure 1: OMNI Surgical System**

### 4.3 TRAINING

Investigators participating in the study must be experienced in using the OMNI 2.0 (OMNI NextGen) Surgical System. All study staff will receive training on the protocol and execution of the study according to applicable regulations and Good Clinical Practices.

## 5 PRIOR INVESTIGATIONS

Several case-series studies have been performed to evaluate the results of ab-interno transluminal viscoelastic delivery and trabeculotomy performed with the OMNI device in patients with open angle glaucoma. These prior investigations were not conducted in the same subject population as defined in this protocol. Thus, the data presented here will not be used for making assumptions for the current study.

Grabska-Liberek, et al reported on 15 eyes (13 patients) with open angle glaucoma. Eight eyes were treated with OMNI surgery alone and 7 eyes underwent OMNI surgery plus cataract extraction (OMNI + CE). Preoperative mean IOP was  $20.13 \pm 4.44$  mmHg (min IOP=13 mmHg, max IOP=38 mmHg). Postoperative IOP decreased to a mean of  $13.90 \pm 4.45$ ,  $14.07 \pm 2.52$ ,  $13.43 \pm 2.95$ ,  $13.71 \pm 2.58$ ,  $12.73 \pm 2.00$ ,  $12.67 \pm 3.32$  and  $12.67 \pm 1.75$  mmHg at 1 week, 1 month, 3 months, 6 months, 1 year, 18 months and 2 years. The number of anti-glaucoma medications dropped from a mean of 2.60 preoperatively to 0.07, 0.20, 0.29, 0.43, 0.82, 1.22 and 1.33. Complications were limited to IOP-spikes (nine eyes), hyphema (six eyes) and fibrin in the anterior chamber (five cases) that were resolved in the first week after surgery. 3 eyes underwent anterior chamber lavage for removal of blood- these patients didn't receive tranexamic acid during the surgery.

[figure not shown]
Martinez-Rubio, et al reported early safety and efficacy of transluminal viscoelastic delivery and trabeculotomy using the OMNI Surgical System in 20 eyes with primary open angle glaucoma, 13 of which were treated with the OMNI device and cataract surgery and 7 who were only treated with the OMNI device. Mean pre-operative IOP was  $24.2 \pm 6.3$  mmHg and the mean number of preoperative antiglaucoma drugs used by patients was 2.7. At 6 months, pressure had been reduced to an average of  $15.9 \pm 3.3$  and medications were reduced to an average of 1.1. Early postoperative complications included one case of transient toxic anterior segment syndrome (TASS) and one case of transient hyphema. Early follow-up data showed a reduction of IOP, with medication reduction, in treatment of moderate glaucoma in adults.

---

 Grabska-Liberek I, et al. OMNI 360 in Open-Angle Glaucoma Treatment: A 24-Month Follow-Up. World ophthalmology congress (WOC) 2019.

**Figure 3: Results for OMNI Surgery (Martinez-Rubio et al)**

## 6 STUDY DESIGN

This is a prospective, multicenter, single-arm, post-market study.

### 6.1 STUDY DEVICE

The study device is the OMNI 2.0 (OMNI NextGen) Surgical System. Subjects enrolled in the study will undergo ab-interno transluminal viscoelastic delivery and trabeculotomy using the OMNI Surgical System.

### 6.2 STUDY SITES

This study will be conducted at up to 10 sites in the United States.

## 7 STUDY ENDPOINTS

### 7.1 EFFECTIVENESS ENDPOINTS

The **Primary effectiveness endpoint** is:

- Proportion of eyes with a  $\geq 20\%$  decrease in unmedicated mean diurnal IOP (DIOP) at the 12-month (or 12-month washout) postoperative examination

[REDACTED]

[REDACTED]

[REDACTED]

**7.2**

[REDACTED]

- | [REDACTED]
- | [REDACTED]
- | [REDACTED]

[REDACTED]

[REDACTED]

**8 STUDY SELECTION CRITERIA**

**8.1 INCLUSION CRITERIA**

At least one eye of each subject should pass the ocular eligibility criteria listed below. Only one eye of each subject is eligible to receive the study procedure:

1. Male or female subjects, 22 years or older at the time of surgery
2. History of uncomplicated cataract surgery and posterior chamber IOL implantation without compromise to the lens capsule, zonular dehiscence/rupture or vitreous prolapse, 6 months or more prior to Baseline Visit.

3. [REDACTED]

[REDACTED]

4. [REDACTED]
6. [REDACTED]
7. [REDACTED]
8. Able and willing to comply with the protocol, including all follow-up visits.
9. Understands and signs the informed consent

## 8.2 EXCLUSION CRITERIA

A subject who meets any of the criteria listed below will not receive the study procedure. Ocular criteria are applicable to study eye and non-ocular criteria are subject-related:

1. [REDACTED]
2. Acute angle closure, traumatic, congenital, malignant, uveitic or neovascular glaucoma
3. Concurrent IOP-lowering procedure other than use of the OMNI Surgical System at the time of surgery (e.g. ECP, CPC, etc.)
4. In the Investigator's judgement, predisposed to significant risk because of washout of ocular hypotensive medications
5. Concurrent ocular pathology or systemic medical condition which, in the Investigator's judgment, would either place the subject at increased risk of complications, contraindicate surgery, place the subject at risk of significant vision loss during the study period (e.g., wet AMD, corneal edema, Fuch's dystrophy, active intraocular infection or inflammation within 30 days prior to Screening Visit, etc.), or interfere with compliance to elements of the study protocol (e.g., returning to Investigator's office for follow-up visits).
6. History of penetrating keratoplasty or another corneal transplant

---

 For combination IOP-lowering medications that consist of two or more IOP-lowering drugs, each IOP-lowering drug component counts as a separate medication.

7. BCVA of logMAR 1.0 (20/200) or worse in the fellow eye not due to cataract
8. BCVA of logMAR 0.4 (20/50) or worse in the study eye not due to posterior capsular opacification (uneventful Nd:YAG laser capsulotomy 6 months prior to baseline is permitted only if there is no vitreous present in or in front of the iris plane at the time of baseline).
9. Participation ( $\leq$  30 days prior to baseline) in an interventional trial which could have a potential effect on the study outcome, as determined by the study investigator
10. Women of childbearing potential if they are currently pregnant or intend to become pregnant during the study period; are breast-feeding; or are not in agreement to use adequate birth control methods to prevent pregnancy throughout the study

## **9.2 NUMBER OF SUBJECTS, DURATION OF FOLLOW-UP AND STUDY DURATION**

[REDACTED]

[REDACTED] in the study will take approximately 9 months. Including the 13-month follow-up period, the study is expected to last 22 months.

## **9.3 INFORMED CONSENT AND POINT OF ENROLLMENT**

The IRB-approved informed consent will be presented and explained to each prospective subject by the investigator or a trained clinical professional. Once the subject has had ample time to read the consent form, has been informed of all aspects of the study, and has had an opportunity to ask questions, the subject will be given a choice to voluntarily confirm his or her participation in the study as documented by completion of the Informed Consent. After signing the Informed Consent and the HIPAA (Health Insurance Portability and Accountability Act) authorization, the subject can then proceed with the screening visit. The subject has the right to withdraw from the study at any time without consequences, as indicated in the Informed Consent Document.

The subject's signed and dated informed consent must be obtained before conducting any study specific procedures that are not part of the standard of care. Subjects are enrolled upon signing the ICD even if they subsequently fail to meet the eligibility criteria.

The principal investigator(s) must retain the original, signed written Informed Consent Document. A copy of the written Informed Consent Document must be given to the subject.

## **9.4 SCREENING VISIT**

After obtaining an understanding of the purpose of this study, then reviewing and signing the Informed Consent Document, all potential subjects will undergo an initial screening examination in order to determine their eligibility for the study. Exams and tests listed in the Screening column of Table 1 should be performed. Refer to Appendix A for instructions for performing the exams.

If a subject does not meet the inclusion/exclusion criteria, he/she may be re-screened after 30 calendar days. Subject should be exited from the study and assigned another subject identification number at the second screening.

Exam data collected on subjects prior to enrollment as part of the routine clinical practice may serve as Screening data as long as it was collected within 15 days prior to the visit. The only exceptions to this are:

- IOP and IOP-lowering medications. These data must be collected at the Screening visit.
- Visual field: Visual Fields conducted per the protocol method (Humphrey 24-2 SITA standard) within 6 months of the screening visit will be acceptable.

### **9.5 WASHOUT OF HYPOTENSIVE MEDICATIONS**

Subjects on ocular hypotensive medication who meet all eligibility criteria at the screening visit will be instructed to discontinue their ocular hypotensive medication regimen, and to return for a Baseline visit after completing the appropriate washout period. The final eligibility assessment will happen at baseline visit.

[REDACTED]

[REDACTED]

## 9.7 SURGICAL PROCEDURE

[REDACTED]

Eyes with complications related to previous glaucoma implants (such as displacement of implant) or IOL (such as posterior capsular rent or vitreous presentation) should be exited from the study. The region where the trabeculotomy procedure is performed (e.g. superior hemisphere) and the extent of trabeculotomy should be recorded on the case report forms.

Surgeons should follow their standard intra-operative and peri-operative medication regimen.

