## **11.2 ANALYSIS POPULATIONS**

The intent-to-treat (ITT) analysis population includes all subjects who are enrolled and treated, regardless of whether or not they have a protocol deviation. The per-protocol analysis population (PP) is a subset of ITT, which includes all subjects who have ab-interno transluminal viscoelastic delivery and trabeculotomy, 12 month IOP (or hypotensive medications washed out IOP if the medications can be washed out) and medication data, and have no clinically significant protocol deviations. It should be noted that the ITT subjects with an uneventful study procedure but with SSIs before the 12-month visit will be included in the PP population even if they do not have the 12-month IOP and medication data. The primary analyses on the primary and secondary endpoint analyses will be carried out on the per-protocol population.

The safety data will be summarized based on the ITT population. The primary and secondary endpoint analyses will also be performed on the ITT population.

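### A treated eye exited under the implant/IOL complication rule in 9.7 drops out of the per-protocol primary analysis and out of follow-up, and no visible rule counts it as a failure

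*Combined protocol and SAP*

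**What the plan says.** Section 9.7 (Surgical Procedure) names eyes whose complications are linked to an earlier glaucoma implant, for example one that has moved, and goes on: "or IOL (such as posterior capsular rent or vitreous presentation) should be exited from the study". The paragraph before this sentence is redacted. The sentence after it concerns recording where, and over what extent, the trabeculotomy was done.

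Section 11.2 defines the analysis sets:

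- The ITT population "includes all subjects who are enrolled and treated, regardless of whether or not they have a protocol deviation".
- The per-protocol (PP) population is a subset of ITT. It requires the study procedure, no clinically significant deviation, and "12 month IOP (or hypotensive medications washed out IOP if the medications can be washed out) and medication data".
- There is one exception to the data requirement: "the ITT subjects with an uneventful study procedure but with SSIs before the 12-month visit will be included in the PP population".
- PP is primary: "The primary analyses on the primary and secondary endpoint analyses will be carried out on the per-protocol population". The same endpoints are also analysed on ITT.

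Four other places bear on the point:

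- Section 9.9 counts subjects with a secondary IOP-lowering intervention as treatment failures and gives them a defined period of follow-up before withdrawal.
- Section 11.4.1 lists imputations that may be used in the ITT analysis for eyes with missing 12-month data and no such intervention.
- Sections 11.5 and 11.5.1 summarise safety on ITT from all available data, with intraoperative events as a separate class.
- Section 13.3 says that everyone enrolled and treated is monitored until the investigation ends.

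**The concern.** The exit rule stands in the surgical section and gives no timing. Inclusion criterion 2 already requires "History of uncomplicated cataract surgery and posterior chamber IOL implantation without compromise to the lens capsule, zonular dehiscence/rupture or vitreous prolapse", and section 9.5 places the final eligibility check at the baseline visit. For the capsule and vitreous, the rule therefore adds most for what is found, or happens, at surgery. In the rule, the word for previous describes the implant and does not say when the complication occurs.

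If the rule can reach an eye after the device has been used, it is a post-treatment exclusion from the primary analysis, triggered by a complication. Such eyes may well do worse than the rest. Removing them from the denominator can then only raise the observed success rate. Their safety follow-up would also end on the day of exit.

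**Working it through.** **1. Path of a treated eye that is exited under 9.7**

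| Question | Text that decides it | Result |
|---|---|---|
| In ITT? | 11.2: enrolled and treated | Yes, if it counts as treated; the visible text does not define that word |
| 12-month data? | 9.7: exited | No |
| In PP by the data requirement? | 11.2 | No |
| In PP by the exception? | 11.2: needs a secondary surgical intervention and an uneventful procedure | No, unless both apply |
| Counted as a failure? | 9.9: secondary IOP-lowering interventions only | No |
| Imputed in the ITT analysis? | 11.4.1: may be performed | Optional |
| Events before exit reported? | 11.5, 11.5.1 | Yes |
| Followed after exit? | 9.7 says exit; 13.3 says monitored for the duration | The two sections conflict |

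In 13.3, withdrawn subjects are set aside only in defining when the investigation is complete, so that clause does not remove the conflict. An eye exited before it counts as treated would be outside ITT, PP and the safety set.

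**2. The plan's own figure**

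Inputs from section 11.1: P0 = 0.40, P1 = 0.55, one-sided alpha 0.025, power 80%, 91 evaluable eyes.

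n = [(1.960·√(0.40·0.60) + 0.842·√(0.55·0.45)) / 0.15]² = 84.50

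With continuity correction: (84.50/4)·[1 + √(1 + 2/(84.50·0.15))]² = 91.05

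This matches 91, so the sample size is not in question. Section 11.4.1 tests against the goal with the binomial distribution. At n = 91 the exact test succeeds at 47 or more responders, since P(X ≥ 47 | 91, 0.40) = 0.0161.

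**3. Effect of dropping k exited eyes**

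Assumptions: 91 treated eyes, all others evaluable, k exited eyes, all of them true failures. The documents give no value for k.

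- m = 91 − k is the PP denominator, and r is the smallest count with P(X ≥ r | m, 0.40) ≤ 0.025.
- *p dropped* = P(X ≥ r | m, 0.40).
- *p as failures* = P(X ≥ r | 91, 0.40), which is the same responders over all 91.
- *False success* = P(X ≥ r | m, 0.40·91/m), the chance that PP succeeds when the true rate over all 91 eyes is exactly 0.40.

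| k | r/m | p dropped | p as failures | False success |
|---|---|---|---|---|
| 0 | 47/91 | 0.0161 | 0.0161 | 0.0161 |
| 1 | 46/90 | 0.0213 | 0.0266 | 0.0262 |
| 2 | 46/89 | 0.0168 | 0.0266 | 0.0257 |
| 3 | 45/88 | 0.0223 | 0.0425 | 0.0406 |
| 5 | 44/86 | 0.0234 | 0.0653 | 0.0613 |

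If instead 91 eyes remain in PP and the exited eyes are added back as failures, 47/91 (p = 0.0161) becomes 47/92 with one (p = 0.0203, still a success) and 47/93 with two (p = 0.0254, not met).

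**The case against.** The case on the other side has five parts.

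- **The rule is about earlier hardware.** It names complications of a previous implant or the IOL and does not mention complications of the study procedure. A reader might infer that it is written to discard procedure complications. The wording allows that for an event at surgery but does not establish it. The rule also has a plain use before treatment: the synopsis admits eyes with an iStent older than 6 months, and no visible criterion covers one that is found displaced. This stands.
- **The timing may be redacted.** The paragraph before the sentence and the baseline-visit section cannot be read, and either may confine the rule to the time before device use. This stands, and a redaction is not a gap in the plan. It would settle the scope of 9.7. It would not change 11.2, where the PP definition can be read and makes no provision for such an eye.
- **Safety events are not dropped.** A reader might infer that these complications vanish from the safety results. They do not: for a treated eye, events up to exit are in the ITT summary. Only follow-up after exit is lost.
- **The ITT analysis covers the eye.** The first imputation in 11.4.1 uses baseline IOP when there are no data after month 3. An eye exited at surgery would then show no reduction and be a non-responder. This is true, but the imputation is optional and ITT is not the primary set.
- **The numbers are boundary cases.** They assume both the count and the outcome of the exits. This stands. With one or two exits the false-success chance is 0.0262 or 0.0257, barely above the nominal 0.025.

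**Conclusion.** The point holds in a limited form. On the visible text, a treated eye exited under 9.7 leaves the primary denominator without being counted as a failure and loses its remaining follow-up, which contradicts 13.3. If such eyes do worse than the rest, the exclusion favours the device.

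The size is unknown because the documents give no exit rate. One exit can decide a result at the boundary (46/90 against 46/91). The false-success chance clearly exceeds 0.025 only with three or more exited eyes that are all failures (0.0406 at three, 0.0613 at five). The documents do not support a claim that the primary result will be materially biased, nor that the rule was meant for complications of the study procedure.

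The conclusion rests on two assumptions: that redacted text does not already confine the rule to eyes not yet treated, and that an exited eye has no 12-month measurement. The change to 11.2 is worth making even if the first assumption is wrong, because it closes the gap whatever the timing in 9.7.

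**What to change.** Reconcile 9.7, 11.2 and 13.3 as follows:

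- **9.7:** state that exit from the study applies only to eyes in which the device has not been used.
- **11.2, ITT:** define treated as the device having been used in the eye, and keep every such eye in ITT.
- **13.3:** keep every such eye in study follow-up.
- **11.2, primary analysis:** include such eyes as non-responders when 12-month data are missing because of a 9.7 complication, whether or not the procedure was uneventful.

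This concerns study participation and counting only. Clinical care of these eyes stays with the investigator.

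The cost is wording in three sections, follow-up of a few eyes, and a possibly slightly lower success rate.
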